#### \* The items are:

Thinking about how you were ten years ago, how are you at:

- a) handling your personal finances (banking, pension, etc)?
- b) thinking about future events and planning ahead?

(Much improved/ A bit improved/ Not much change/ A bit worse/ Much worse)

- 4. Self-report of difficulty in finance and planning alone (since these questions had an AUROC of 0.9 with the caveat about self-report).
- 5. Multiple imputation of the missing dementia outcome will be carried out following the same approach as in the primary analysis section 4.4. Sensitivity analyses to the imputation will include assuming all missing have/do not have dementia.

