## **Primary Research Objective:**

Amongst older adults (60-85 years) both with and without cognitive impairment, the primary research objectives are:

- to estimate the effectiveness and cost-effectiveness of the Active Brains digital intervention (compared with usual care) in maintaining cognitive functioning (assessed by verbal reasoning performance).
- 2) to estimate the effectiveness and cost-effectiveness of the Active Brains digital intervention (compared with usual care) in maintaining cognitive functioning (assessed by verbal reasoning performance) when supported as necessary by a trained behavioural facilitator.

The primary outcome (effectiveness) measure at one year is an online version of the Baddeley Verbal Reasoning task.

At the five year follow-up point\*, a further primary objective is to estimate the effectiveness of the Active Brains digital intervention in delaying dementia. This will be determined in the following way:

1. If there is a notes diagnosis of dementia participants will be classed as having dementia.

As recording in notes is often sub-optimal, as sensitivity analyses, we will use the following methods to ascertain the dementia outcome:

- 2. Self-report item "Has a doctor or other medical worker ever said that you have dementia?" (Y/N) as collected in baseline and year 1 and year 5 follow-up online/paper measures.
- 3. Evidence of significant decline in Baddeley (baseline to follow-up) **AND** evidence of functional deterioration (EITHER: a) significant change in self-report IQCODE (baseline to

follow-up) OR b) two self-report questions on difficulty in finance and planning\*. These items are collected in year 5 online/paper measures.

\* The items are:

Thinking about how you were ten years ago, how are you at:

- a) handling your personal finances (banking, pension, etc)?
- b) thinking about future events and planning ahead?

(Much improved/ A bit improved/ Not much change/ A bit worse/ Much worse)

Self-completed IQCODE will be used as it is likely to provide the most complete data. However, we will also explore the agreement between self-completed IQCODE and informant completed IQCODE among willing contacts (where provided), how these relate to other outcomes, and the implications of using self-completed or informant completed measures.

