We will also explore the implications of using decrements in the other computerised tests (spatial working memory, attention, and verbal short-term memory) combined with IQCODE in indicating a diagnosis of dementia.

4. Self-report of difficulty in finance and planning alone.

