## 4.5.10 Diagnosis of dementia

Diagnosis of dementia will be obtained from notes review. This will be analysed using logistic regression, adjusting for the same covariates as in the primary analysis.

The primary definition of dementia will be based on:

1. If there is a notes diagnosis of dementia participants will be classed as having dementia.

As sensitivity analyses, we will use the following methods to ascertain the dementia outcome:

- 2. As recording in notes is suboptimal, consider self-report item "Has a doctor or other medical worker ever said that you have dementia?" (Y/N) this data currently collected in baseline and year 1 and year 5 follow-up online/paper measures.
- 3. Evidence of significant decline in Baddeley (baseline to follow-up) **AND** evidence of functional deterioration (**EITHER**: a) significant change in self-report IQCODE (baseline to follow-up) **OR** b) two self-report questions on difficulty in finance and planning\* (NB the Caerphilly study was based on informant not self-report). Difficulty in finance and planning items collected in year 5 online/paper measures.

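### Sensitivity definition 4 of five-year dementia looks back ten years with no baseline functional measure in its model, so pre-entry worsening can count and weaken the comparison

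*SAP*

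**What the plan says.** The primary five-year definition of dementia is a diagnosis in the notes (SAP 1.4.1 and 4.5.10). Because recording in notes is imperfect, both documents list alternative definitions as sensitivity analyses.

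- **Definition 4** is, in the SAP, "Self-report of difficulty in finance and planning alone (since these questions had an AUROC of 0.9 with the caveat about self-report"; the protocol, under Primary Research Objective, has "Self-report of difficulty in finance and planning alone".
- **The items** start with "Thinking about how you were ten years ago, how are you at" and offer five answers: "Much improved/ A bit improved/ Not much change/ A bit worse/ Much worse". Neither document says which answers count as difficulty, or whether one or both items must meet the criterion.
- **Timing.** The SAP says "Difficulty in finance and planning items collected in year 5 online/paper measures"; the protocol says "These items are collected in year 5 online/paper measures". For the self-reported diagnosis in definition 2, by contrast, the SAP says "this data currently collected in baseline and year 1 and year 5 follow-up online/paper measures". Neither measures table lists the finance and planning items at any visit.
- **Definition 3** can use the same two items, but only together with "Evidence of significant decline in Baddeley (baseline to follow-up").
- **Model.** Logistic regression with the covariates of SAP 4.4: baseline Baddeley score, age, gender, IMD score, number of comorbidities and polypharmacy. The protocol's Statistical analysis section says that every regression model will control for baseline values.

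**The concern.** Asked at year 5, a ten-year look-back covers roughly five years before randomisation and five after. Definition 4 has nothing to separate the two. Someone whose handling of money became much worse two years before joining, and who has been stable since, gives the same answer as someone with the same decline after joining. Eligibility excludes diagnosed dementia but not earlier difficulty with finances or planning. Elsewhere the plan anchors change to the trial period: definition 3 requires Baddeley decline from baseline, and the IQCODE analysis in SAP 4.5.3 adjusts for baseline IQCODE. Definition 4 is the exception.

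The alternative definitions are there to show whether the notes-based result survives poor recording. If definition 4 is weakened by construction, a smaller effect under it is ambiguous: it could mean a fragile primary result, or merely decline that predates the trial.

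**Working it through.** **Inputs from the plan (SAP 2.2, 2.1 and 4.4).** Five-year dementia 25% control against 20% intervention, two-sided alpha 0.05, 80% power, 60% followed up, allocation 1:1:1.

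**The plan's own figure.** With pooled variance and no continuity correction, and mean risk 0.225:

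n = [1.96·√(2·0.225·0.775) + 0.8416·√(0.25·0.75 + 0.20·0.80)]² / 0.05² = (1.1575 + 0.4961)² / 0.0025 ≈ 1094.

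This matches. Then 2 × 1094 = 2188 per arm, 2188/0.6 = 3647 per arm and 3 × 2188/0.6 = 10,940 in total, all as stated.

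**Dilution.** Let q be the share already worse, before entry, by whatever cut-off is adopted. The documents give no value for q, so a range is shown. Assume that q is the same in each arm, is independent of later decline, and that these people still answer as worse at year 5. The documents give no rates for these two items either, so 25% and 20% stand in for the within-trial risks. Then:

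- control risk = 1 − (1 − q)(0.75)
- intervention risk = 1 − (1 − q)(0.80)
- difference = (1 − q) × 0.05

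Power = Φ{[difference·√n − 1.96·√(2p̄(1 − p̄))] / √(p₁(1 − p₁) + p₂(1 − p₂))}, where p̄ is the mean of the two risks p₁ and p₂.

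At q = 12.5% and n = 2188: (0.04375 × 46.78 − 1.96 × 0.6607)/0.6600 = 1.14, so power is 87%.

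| q (assumed) | Control | Intervention | Difference, points | RR | OR | Power, 2188 per arm |
|---|---|---|---|---|---|---|
| 0 | 25.0% | 20.0% | 5.0 | 0.80 | 0.75 | 98% |
| 12.5% | 34.4% | 30.0% | 4.4 | 0.87 | 0.82 | 87% |
| 25% | 43.8% | 40.0% | 3.75 | 0.91 | 0.86 | 71% |
| 40% | 55.0% | 52.0% | 3.0 | 0.95 | 0.89 | 51% |

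At q = 25%, 0.25/0.4375 = 57% of control cases predate randomisation. With 1094 per arm, the number planned for each of the MCI and AACD groups, power falls from 80% at q = 0 to 43% at q = 25%.

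**What baseline IQCODE adjustment recovers.** The q = 25% case was simulated with 2188 per arm, and the logistic model was fitted with and without a baseline score that is shifted upwards in people who declined before entry. Power rose from about 70% to between 75% and 84%, depending on how closely the score tracks prior decline, and the OR moved away from 1. A shift of one SD gave about 75%; with half an SD the gain almost vanished.

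**The case against.** Several objections have force.

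- **A reader might infer that definition 4 counts any worsening.** The documents do not say so, because no cut-off is given. A stricter cut-off would reduce the carry-over but not remove it. The missing rule is a gap in itself, since the definition cannot be coded without one.
- **Pre-entry worsening need not be fixed.** The items compare the person's state at year 5 with a fixed earlier time, so someone who declined before entry and improved on the intervention could move to a better answer. The table rules this out, and also assumes independence from later decline; neither assumption comes from the documents.
- **q is unknown.** It is tempting to say that pre-entry worsening must be common in the cognitive decline trial. Eligibility there rests on a below-norm Baddeley score, which is a level and not evidence of recent or self-perceived decline. At q = 12.5%, power with both groups combined still exceeds the planned 80%.
- **Only one sensitivity analysis is affected.** Definition 2 has a baseline measurement, definition 3 has the Baddeley condition, and the SAP already attaches a caveat about self-report to definition 4. That caveat does not deal with the time window.
- **Collection only at year 5 is an inference,** though a fair one from the stated timing. The baseline self-report IQCODE uses a similar improved-to-worse scale, but the documents do not say that it contains these two items.

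None of this supplies definition 4 with a way to tell pre-entry from within-trial worsening.

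**Conclusion.** The point holds as a limited one. As written, definition 4 cannot separate worsening before randomisation from worsening during the trial, and its model lacks the baseline control that the protocol promises for all regressions. The expected result is attenuation and lower power. Under the stated assumptions the direction holds for every q above zero, with the risk difference shrinking by the factor (1 − q). The table's size is illustrative only.

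Two stronger readings are not supported. A reader might infer that the analysis is biased in favour of an arm; randomisation balances pre-entry decline in expectation, so it is not. A reader might also infer that the five-year dementia result or the sample size is compromised; both rest on the notes-based definition and its planned rates, which this does not touch.

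**What to change.** In SAP 4.5.10:

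1. Add the baseline self-report IQCODE score, which the measures table shows as collected in all arms, as a covariate in the logistic model for definition 4, and for definition 3 where it rests on the finance and planning items.
2. State which answers count as difficulty and whether one or both items are required.
3. State that definition 4 includes pre-randomisation change, so that a weaker effect under it is not by itself evidence against the notes-based result.

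The cost is a few sentences in the SAP and no new data collection. The adjustment reclassifies nobody and recovers only part of the precision. It also makes the definition 4 odds ratio conditional on one more covariate than the notes-based one, which should be noted when the two are compared.

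A retrospective question at year 5 about whether the difficulty was already present on joining is not recommended. Participants know their allocation (SAP 2.3), so dating onset by recall could differ by arm, and restricting to onset after joining would drop people who were mildly worse at entry and then progressed.

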#### 4.5.11 Death

Death will be obtained from notes review, or reported by the practice, supporter or relative. This will be analysed using logistic regression, adjusting for the same covariates as in the primary analysis.

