#### Randomisation

Patients will be randomised online using the study software. They will have an equal chance of being in each of the three groups in each of the two trials (the trial among those with cognitive impairment, and the trial among those with no cognitive impairment). Once randomised, participants will be informed of their group allocation (they will also be emailed this information). If participants are in one of the treatment arms they will be taken directly to Active Brains where they can begin the intervention. These participants can then use Active Brains as much as they would like to over the course of the study. The central facilitator will be notified by email when a participant is randomised to the support arm of the trial, so that they know to expect to provide support to the participant in the coming weeks.

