### **Central Facilitator Support**

Patients in the group receiving support from a central facilitator (in addition to the website) will be offered a brief (10 minute) telephone support call 2 weeks after they begin the study. In this support call they will discuss the cognitive/lifestyle changes that they are choosing to try. Patients will be offered two more support contacts by phone (up to 10 minutes) or email to support them in making behavioural changes. Should the participant not yet have

accessed Active Brains at the time of contact, the supporter will check whether the participant is having any technical difficulties and/or talk through any other barriers to getting started.

For patients who feel the need, up to 7 further email or phone contacts can be arranged. In the feasibility study only one participant requested additional contact beyond the three initial calls (n = 120 in support arm). In our previous studies only around 10-15% of patients have required this further support.

The central facilitator will use the CARE (Congratulate, Ask, Reassure, Encourage) approach to provide support to patients, which is based on Self-Determination Theory [52] and designed to promote autonomous motivation for making behavioural changes. The CARE approach has been used successfully in our previous trials and has been shown to be acceptable to patients and staff supporting patients [53]. Supporters will also provide brief technical website support to all participants as required throughout all contact points (e.g. advice on logging in problems). To maximise fidelity of support delivery, a 'checklist' of the CARE approach is provided in the supporter training materials that supporters are encouraged to use to guide their calls with participants. This will also include space to write notes about these interactions. As a means of fidelity check, supporters will be encouraged to share the completed checklists/notes from one or two of these anonymous interactions with the research team. A member of the research team with expertise in the CARE approach will provide feedback to the supporter as appropriate.

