nuts a	and oils) [64]												
Brain	training behaviours					Х	Х	Х	Х	Х	Х	Х	Χ
	nt rated adherence to						Х	Х	Х				
	ges in behaviour and list												
_ ~	riers they felt												
	buted to their												
	ence (measured with												
	ETS questionnaire) [65]												
	Geriatric Depression	Х	Х	Х	Х	X 	X 	X 	X 				
	[66, 67]	^	^	^	^	^	^	^	^				
	efficacy for exercise	Χ	Х	Х	Х	Х	Х	Х	Х				
	-	^	^	^	^	^	^	^	^				
scale	S Social Support	Χ	Х	Х	Х		-						
	• •	٨	^	^	^								
Surve	ey – 8 item [69, 70]												

Social Support for Exercise scale [71]						Х	Х	Х				
Locus of Causation in	Х	Х	Х	Х	Х	Х	Х	Х				
Exercise [72]												
Technology Acceptance						Χ	Χ	Χ				
Model Perceived Ease of												
Use scale [73-75]												
Pedometer use/purchase					X	X	Х	X				
Objective patient data												
Usage of the Active Brains		Χ	Х	Х		Х	Х	Х		Х	Χ	Х
website throughout (including												
what components viewed												
and any data entered online												
such as at goal reviews).												
Objective supporter data												
Supporters' Usage of Active			X				Х				Χ	
Brains website (throughout												
study)												
Emails sent to participants			X				Х				Χ	
throughout study												
Qualitative data												
Interviews with patients about					Xa	Xa	Xa					
their experiences of the study												
and/or intervention												
Interviews with Central						)	X					
Support Facilitators about												
their experiences of the study												
and intervention												
Proxy-Measures (not cohort	group						4	_	1	.,	0.4	
		Bas	seline			Years	1 and	5		Year	s 2-4	
Informant Questionnaire on												
Cognitive Decline in the							X					
Elderly (IQCODE) (short												
form) [56]												
Quality of Life (EQ5D5L-												
proxy version 2) to be						2	Χ					
completed by the nominated						•						
contact person (if necessary)												
IADL proxy version to be												
completed by the nominated							Χ					
contact person (if necessary)						-						

\*=notes a measure collected at notes review at Year 1 **or** 5 (depending on when notes review conducted).

[figure not shown]
<sup>1 = collected at year one only (not year five also)

<sup>a = Year 1 only; process interviews to be conducted 2-12 months after commencement of study

b = baseline only

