## 2.2 Trial power and sample size

## **Cognitive decline trial**

For the primary outcome of cognitive decline at 5 years we assume an alpha of 0.05 and 80% power to detect a standardised effect of 0.15. This requires 698 per group for the MCI subgroup and the same again for the AACD subgroup. Assuming that 60% will be available to provide follow-up within 5 years, that rises to 698\*3/0.6=3490 participants with MCI and the same with AACD per group or 6980 in total.

Although the reduction in cognitive decline as assessed using the Baddeley reasoning test is the primary outcome at one year, the limiting factor in the sample size calculation for those with cognitive impairment is the progression to dementia at 5 years (see outcome definition in section 4.5.9). We assume a 5% annual progression rate to dementia among those who are cognitively impaired. With alpha 0.05 and 80% power, we aim to detect a difference of 5% after 5 years (20% intervention and 25% control) in those diagnosed with dementia. This means we would need 1094 in each of the MCI and AACD groups or a total of 2188. Assuming that 60% will be available to provide follow up in 5 years requires 3647 in each of the 3 study groups or 10940 in total.

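### SAP 4.5.11 lets a supporter's unconfirmed report count as a death, and only the Active Brains plus support arm has supporters, so deaths may be ascertained unequally

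*SAP*

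**What the plan says.** SAP 4.5.11 defines the outcome by source: "Death will be obtained from notes review, or reported by the practice, supporter or relative". The four sources are alternatives, with no order of precedence and no confirmation step. On analysis it adds only: "This will be analysed using logistic regression, adjusting for the same covariates as in the primary analysis". SAP 3.5 compares each active arm with usual care at the 5% level.

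The supporter belongs to one arm. Under Randomisation the protocol states: "The central facilitator will be notified by email when a participant is randomised to the support arm of the trial". Under Central Facilitator Support it begins: "Patients in the group receiving support from a central facilitator (in addition to the website) will be offered a brief" telephone call two weeks after starting, and continues: "Patients will be offered two more support contacts by phone (up to 10 minutes) or email to support them in making behavioural changes". Up to seven further contacts can be arranged, but uptake was very low: "In the feasibility study only one participant requested additional contact beyond the three initial calls (n = 120 in support arm").

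The other routes are open to all three randomised arms. Protocol Table 2 marks mortality in the usual care, Active Brains and AB + Support columns as "a measure collected at notes review at Year 1" or 5. Under Non serious AEs and exemptions, deaths judged unrelated to the trial are sent in on an End of Study form, with no restriction by arm. Under Measures, any participant may nominate a contact person at sign-up, who is approached at years 1 and 5 if the participant cannot be reached.

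**The concern.** A mortality comparison between randomised arms is fair only if a death has the same chance of being found in each arm. Here a death that notes review, the practice and relatives all miss can still be counted in Active Brains plus support, because a supporter heard of it. The same death in usual care, or in Active Brains alone, would go unrecorded. The asymmetry runs one way: the supporter route can add deaths to one arm and cannot add them to another.

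Mortality is a listed secondary objective. Unrelated serious adverse events need not be reported as such, so the modelled death endpoint carries much of the trial's information on overall harm. A small artificial excess in the supported arm would be awkward to interpret, and it is avoidable.

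**Working it through.** **Step 1. Is the source really confined to one arm?** The protocol uses supporter for the central facilitator and contact person for the nominated friend or relative. Table 2 marks supporters' website usage and emails to participants in the AB + Support column only. One line under Central Facilitator Support mentions technical help for all participants, but it refers to the contact points described in that section, which are those of the supported arm. So yes.

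**Step 2. Can the shared routes be taken as complete?** The documents give no completeness figure for notes review or practice reporting. SAP 4.5.10 plans multiple imputation for missing values of the dementia outcome, whose primary definition is also notes-based, so the SAP expects some gaps in notes-based data. SAP 4.5.11 has no matching provision for death.

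**Step 3. Size.** The plan states no mortality figure to reproduce. As a check on the arm size used below, SAP 2.2 gives 2188 per arm before loss, then "Assuming that 60% will be available to provide follow up in 5 years": 2188/0.6 = 3646.7, which agrees with its 3647.

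Inputs:
- From the documents: n = 3647 per arm (cognitive decline trial). The share unavailable, u, is 0.30 at year 1 (protocol, 70% follow-up) and 0.40 at year 5 (60% follow-up). These are general follow-up allowances, used here as a stand-in for missing notes and practice information.
- Assumed: annual mortality m = 1–3%, equal in all arms; a share q = 0.25 of one year's deaths falls in the support-contact period; supporters learn of a share s = 0.10–0.50 of the otherwise missed deaths in that period.

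Formulas, for follow-up of T years:
- Deaths found by shared routes = n·m·T·(1 − u)
- Extra deaths, supported arm only = n·m·q·u·s
- Relative inflation = q·u·s / [T·(1 − u)], in which m cancels

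Year 1 (T = 1, u = 0.30):
- s = 0.10: 0.25 × 0.30 × 0.10 / 0.70 = 1.1%
- s = 0.50: 0.25 × 0.30 × 0.50 / 0.70 = 5.4%
- Extra deaths: from 3647 × 0.01 × 0.25 × 0.30 × 0.10 = 0.3 to 3647 × 0.03 × 0.25 × 0.30 × 0.50 = 4.1, on 26 to 77 deaths found by shared routes

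Year 5 (T = 5, u = 0.40):
- s = 0.10: 0.25 × 0.40 × 0.10 / (5 × 0.60) = 0.3%
- s = 0.50: 0.25 × 0.40 × 0.50 / (5 × 0.60) = 1.7%
- Extra deaths: from 3647 × 0.01 × 0.25 × 0.40 × 0.10 = 0.4 to 3647 × 0.03 × 0.25 × 0.40 × 0.50 = 5.5, on 109 to 328 found

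With no true effect, a two-sided 5% unpooled normal test on these risks, with p0 = m·T·(1 − u) and p1 = p0 + m·q·u·s, rejects in 5.0–6.3% of trials at year 1 and 5.0–5.6% at year 5. If u = 0, or if only shared sources count, the apparent odds ratio is 1.000 and the rate is 5.0%.

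**Step 4. Does the handling of unknowns change this?** Hardly. If people with unknown status are left out of the model, the apparent odds ratio is exactly 1 plus the relative inflation. If they are classed as alive, it is slightly larger: at most 1.055 at year 1 and 1.018 at year 5 over these ranges.

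**The case against.** The strongest reply is that a supporter's report matters only where every shared route fails. Participants are recruited through practices, notes review for mortality is planned in all three randomised arms, and practices report deaths in all of them. Three short contacts, some possibly by email, give a supporter little chance to learn of a death that the practice has missed. A report of death also leaves little room for unblinded judgement. All of this stands, and it limits the size. It does not remove the asymmetry in the rule, and completeness is nowhere stated.

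A reader might infer four stronger things that the documents do not support:
- That 40% of participants will lack death information. The same 60% allowance is applied to the online reasoning task and is not described as notes-review coverage. Applying it to first-year deaths would also mix time points, since the year-1 allowance is 30%.
- That supporters would learn of every missed death in the contact period. Nothing suggests this.
- That relatives are also a source specific to the supported arm. Relatives can be reached in every arm, through the contact-person procedure and the postal and telephone follow-up of non-responders.
- That death is the only all-cause harm measure. Hospitalisation is also taken from the notes in all three arms, though for the economic analysis.

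**Conclusion.** The point holds as a defect in the endpoint rule: SAP 4.5.11 permits unequal ascertainment of death between Active Brains plus support and usual care. It would go too far to say that the comparison is biased. The direction of any bias is known (more counted deaths in the supported arm), but its size is not. It is nil with complete notes and practice coverage. Under the assumptions shown, it is about 1–5% of counted deaths at year 1 and 0.3–1.7% at year 5, with the lower ends more plausible given how light the contact is. The estimates depend on the assumed contact-period share, the supporters' detection rate, and the use of general follow-up loss as a proxy for missing notes. This is a minor point on a secondary endpoint, worth making because it costs so little to correct.

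**What to change.** In SAP 4.5.11:
- Base the modelled death outcome on sources open to all three arms: notes review, practice report, and the contact person approached under the common follow-up procedure.
- Treat a supporter's report as a prompt to check with the practice, and count the death once the practice confirms it.
- Record the source of every death and list unconfirmed supporter-only deaths by arm.
- In the main model, treat those participants as missing, not as survivors, and state how all other participants without a notes review are classed.
- Report an all-sources analysis as a sensitivity analysis.

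The cost is a few sentences in the SAP, a source field, and an occasional query to a practice. The drawback is that a few genuine deaths known only to a supporter leave the main model; the listing and the sensitivity analysis keep them visible.
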